Given the importance of plasmin and hyperfibrinolysis in the pathophysiology of chronic subdural hematomas, interrupting its action and the vicious cycle it propagates seems an ideal therapeutic target. Tranexamic acid is a synthetic lysine amino acid derivative. It binds to the fibrin binding sites on plasmin or plasminogen and prevents its interaction and degradation of fibrin. This effect on the neo-membranes of chronic subdural hematomas should prevent rebleeding and the re-accumulation of the subdural hematoma.

Supporting Data

Kageyama et.al. showed the safety and potential efficacy of treating chronic subdural hematomas in their retrospective study of 21 patients. There were no recurrences in their 21 patients. Vujkovac et.al. also showed that tranexamic acid could be used safely and effectively in their case report of a hemodialysis patient who begun therapy following another recurrence after the third operation. The hematoma completely resolved and the patient made a complete recovery.

Tranexamic acid has been shown to be safe and effective in reducing blood loss and transfusions in a number of types of surgery, reduced mortality and need for urgent surgery in patients with GI bleeding and reduced bleeding associated with menorrhagia and pregnancy. Adverse effects are generally mild. Thought there is a theoretical increased risk of thromboembolic complications, multiple randomized controlled trials have not shown an increased risk (McCormack, Dunn, Katsaros, Barer, Benon). Furthermore, in a study of over 3000 gynecologic patients using tranexamic acid, Bekassy et.al. had no thromboembolic complications. This is likely because tranexamic acid has been shown to not have an effect on plasminogen in the vein wall (Astedt).

Tranexamic acid for cSDH – A Pilot Study on the Safety of Tranexamic Acid for the Chronic Subdural Hematoma Population

Study Design

This study is a single center single armed study of 50 patients to determine the safety of tranexamic acid in the chronic subdural hematoma population following surgical drainage of chronic subdural hematomas. This will be compared to historical controls. This study intends to be a prerequisite to a large nationally funded randomized control trial.

Selection and Enrollment of subjects

Inclusion Criteria:

- all patients undergoing intervention for cSDH including drainage
- cSDH will be defined as hematoma on CT imaging that is predominantly isodense to hypodense to brain
- 18-85 years of age

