-First postop dosing will start 8 hours after preop dose is given.

All patients will have creatinine monitored daily while on study drug. Patients with creatinine > 1.4 will have dosage adjustments as follows:

Table 1. Dosage of LYSTEADA in Patients with Renal Impairment

LYSTEADA		
Serum Creatinine (mg/dL)	Adjusted Dose	Total Daily Dose
Cr above 1.4 and \leq 2.8	1300 mg (two 650 mg tablets) two times a day for a maximum of 5 days during menstruation	2600 mg
Cr above 2.8 and \leq 5.7	1300 mg (two 650 mg tablets) once a day for a maximum of 5 days during menstruation	1300 mg
Cr above 5.7	650 mg (one 650 mg tablet) once a day for a maximum of 5 days during menstruation	650 mg

Prohibited Interventions

Therapeutic anticoagulation

Tranexamic acid for cSDH – A Pilot Study on the Safety of Tranexamic Acid for the Chronic Subdural Hematoma Population

Clinical and Laboratory Evaluations

Presentation Day 0- CT scan, NIH stroke scale, pregnancy test, informed consent, modified Rankin Score (mRS)

Postop-
Day 1 CT Scan

Day 14 clinical follow-up, CT scan

Follow-up Day 30- CT scan, NIH stroke scale, mRS

Timing of Evaluations

Registration- the start of the screening process when the study team is notified of a potentially eligible subject

Pre-Enrollment- all screening evaluations will be performed prior to enrollment

Enrollment- will occur prior to surgical intervention or receiving experimental medication

Medication period- Patients will continue on medication from immediately preoperatively to three days postoperatively or until discharge

Post Medication period- follow-up will continue until the patient is discharged from the neurosurgeon's care

Management of Adverse Events

All adverse events will be closely monitored and evaluated

Management of recurrent bleeding: recurrent SDHs will be managed according to best practices as determined by the treating physician

Criteria for Intervention Discontinuation

1. patient unable to tolerate side effects
2. thromboembolic complication including stroke, MI, DVT or PE
3. if in the investigator's judgment, withdrawal from the trial will be in the patients best interest
4. consent is withdrawn by the patient or their legal representative

End Points

1* Incidence of medication related complications including stroke, MI, DVT, or PE and other drug related adverse events

2- Return to OR for same sided surgery

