2* Postop hematoma expansion, functional outcome (mRS, NIHSS) discharge location, LOS, volume of hematoma at 30 days

Tranexamic acid for cSDH – A Pilot Study on the Safety of Tranexamic Acid for the Chronic Subdural Hematoma Population

Data Points

Age, presenting symptom, admission GCS, language and motor function, preoperative living situation, width of hematoma, visible septations present, extent of MLS, operative approach, drain used, new preoperative deficit, immediate postop hematoma width, LOS, discharge GCS, language and motor function, discharge location, width of hematoma on follow up imaging, medication not tolerated, medication side effects, thromboembolic complications, other complications, blood loss, NIH stroke scale Day 0 and 30, mRS day 0 and 30

Statistical Data Analysis

Frequencies will be reported for ordinal and categorical variables. Descriptive analyses of central tendency (mean) will be used for continuous variables. Nonparametric tests will be used for statistical comparison, including the Kruskal-Wallis rank-sum test for multiple groups and the Mann-Whitney U test for 2 groups. Data tabulation and analysis will be analyzed using R statistical software version 3.4.2 (R Foundation for Statistical Computing, Vienna, Austria). Chi-square test, analysis of variance (ANOVA), and multivariate linear and log-linear regression models where appropriate. A P value < 0.05 will be considered statistically significant. P values for difference among time point means (preoperative, postoperative days 3, 7 and 30) to be determined by ANOVA.

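### Any P < 0.05 may be called significant across 8 endpoint items and an open-ended set of further tests, with no designated test, hierarchy or exploratory label

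*Combined protocol and SAP*

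**What the plan says.** The Study Design section describes the trial in these words: "This study is a single center single armed study of 50 patients". It adds: "This will be compared to historical controls". It also presents the study as a step towards a large randomised trial.

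End Points has three entries:

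- Marked `1*`: "Incidence of medication related complications including stroke, MI, DVT, or PE and other drug related adverse events".
- Marked `2-`: "Return to OR for same sided surgery".
- Marked `2*`: "Postop hematoma expansion, functional outcome (mRS, NIHSS) discharge location, LOS, volume of hematoma at 30 days".

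The Statistical Data Analysis section begins with frequencies and means. It then calls for nonparametric comparisons, "including the Kruskal-Wallis rank-sum test for multiple groups and the Mann-Whitney U test for 2 groups", followed by chi-square tests, ANOVA and regression models at the analyst's discretion. It gives one criterion for all of these: "A P value < 0.05 will be considered statistically significant". It ends with an ANOVA across four time points and does not name the outcome to be analysed.

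The document does not say which endpoints receive a P value, which groups are compared, or which result carries the study's inference.

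**The concern.** A 5% threshold controls the error rate of one test fixed in advance. Applied to each of several endpoints, it allows any of them to produce a result the plan calls significant, and the chance that at least one does so by luck rises with the number of tests. Here that number has no upper limit, because the groups and the regressions are not specified.

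Two details add to this. Same-sided return to the operating room corresponds to the second item under Study Objectives, but its label, `2-`, falls between `1*` and `2*`. The reader cannot tell whether it is a second primary endpoint or a secondary one. The Kruskal-Wallis test is meant for more than two groups, while the design defines one treated arm and a historical comparator.

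A chance finding on a secondary outcome, reported as significant, could enter the case for the later randomised trial with more weight than it deserves.

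**Working it through.** The plan states no family-wise error rate and gives no derivation for its 50 patients, so there is no figure of its own to reproduce.

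**Inputs**

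- Per-test threshold: 0.05 (Statistical Data Analysis).
- Endpoint items as written: 1 safety item + 1 return to the operating room + 6 others (expansion, mRS, NIHSS, discharge location, length of stay, 30-day volume) = 8.
- If the safety item is split into stroke, MI, DVT, PE and other drug-related events: 5 + 1 + 6 = 12.
- Assumptions, not in the plan: every item is tested once, and no true difference exists on any of them.

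**Independent tests.** The chance of at least one false positive in k tests is 1 − 0.95^k.

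- k = 8: 1 − 0.95^8 = 1 − 0.663 = 0.337.
- k = 12: 1 − 0.95^12 = 1 − 0.540 = 0.460.
- k = 13 (12 items plus one overall time-point ANOVA): 1 − 0.95^13 = 0.487.
- Passing one half requires k > ln 0.5 / ln 0.95 = 13.5, that is, at least 14 tests.

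**Correlated tests.** Related endpoints, such as mRS and NIHSS or expansion and volume, will not be independent. Simulation of equally correlated normal test statistics (two-sided, 200,000 draws) gave:

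| Tests | Independent | Correlation 0.3 | Correlation 0.5 |
|---|---|---|---|
| 8 | 34% | 30% | 25% |
| 12 | 46% | 40% | 32% |

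**Rare events.** Tests on sparse events reject less often than 5%. Assume 50 treated against 50 control patients and a rate of 1%, 2% or 5% for each of the four thromboembolic events. The chi-square test then has an actual size of 0.0019, 0.0130 or 0.0434, and Fisher's exact test is lower still. For 12 tests, 1 − (1 − a)^4 × 0.95^8 gives 0.342 at a = 0.0019 and 0.444 at a = 0.0434. Across both tests and all three rates, the range is about 34% to 44%. The 46% figure is therefore an upper value for 12 tests.

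**What cannot be counted.** The plan gives no number for the group comparisons or the regressions. They could raise these figures by an amount the documents do not allow one to compute.

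**The case against.** The strongest reply is that this is a safety pilot. It claims no confirmatory error rate, and the later randomised trial would test efficacy itself. That stands as a limit on the consequence: the harm is over-interpretation. It does not rescue the wording, because a plan with no confirmatory aim has no need to declare significance, and the second study objective is phrased as a question of effect.

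A second reply is that categorical variables are to be reported as frequencies, so the safety events, return to the operating room, mRS and discharge location may only be described. This stands in part. The same paragraph also names chi-square tests and regression, so description is not clearly the limit, but the calculations above are conditional on testing.

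Several stronger readings are tempting, and the documents do not support them:

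- A reader might infer that at least one false claim is likely. Twelve independent true-null tests give 46%, and adding the ANOVA gives 48.7%; both are below one half.
- A reader might count 12 tested endpoints. The safety endpoint is written as one item, and nothing says each event type is tested separately.
- A reader might infer that any groups must be formed after the fact. Historical controls fit a two-group Mann-Whitney test, and Data Points lists operative approach, drain use and septations as planned variables. The fair criticism is that the groups are not named.
- A reader might add six pairwise time-point tests. The plan specifies only an ANOVA. If its outcome is hematoma size, a change after drainage is expected, and rejecting that null would not be a false positive.

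The `2-` label may be a typing or text-extraction artefact, and the order of the objectives partly settles its place. It is a side point.

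**Conclusion.** The concern holds as a gap in labelling and pre-specification. Followed as written, the plan lets any endpoint, group comparison or regression with P < 0.05 be called significant, with nothing to separate a planned inference from an exploratory one.

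On the 8 items as written, the chance of at least one false positive is about 34% under independence, or about 25% to 30% at the correlations examined. It reaches at most about 46% if the safety item is split into five. Each figure assumes that every item is tested and that no true differences exist. The chance is lower if some endpoints are only described, and further unnamed tests would add an unknown amount.

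**What to change.** Replace the significance sentence. State that, in this single-arm pilot, endpoints are reported as estimates with 95% confidence intervals, and that all P values are nominal and exploratory and are not called statistically significant.

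If the sponsor wishes to keep one formal test, name it in advance and give that endpoint one explicit rank. Same-sided return to the operating room matches the second objective and is a natural candidate, although safety is the first objective and the endpoint marked `1*`. The plan would also have to state the time window and the comparator, since End Points gives no window and the historical controls are not specified. Naming one test removes the multiplicity. It does not by itself guarantee a true 5% error rate against non-randomised controls.

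Restrict the Kruskal-Wallis test to groups named in advance and labelled exploratory, or delete it.

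The cost is analysis wording only, with no change to patients, visits or data collection. The small downside is that fewer results can be called significant.

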Exclusion Criteria

- cSDH not requiring surgical drainage
- patients undergoing bedside twist drill craniostomy
- medically unstable for surgery
- patients requiring long-term anticoagulation- unable to stay off for less than 30 days
- patients not expected to survive to the completion of follow-up
- patients comatose prior to the initiation of treatment
- history of thromboembolic problem including stroke, MI, DVT, PE
- pregnant
- minor
- allergy/sensitivity to tranexamic acid
- irreversible coagulopathy
- known clotting disorder
- bilateral hematomas with both requiring drainage
- incarcerated
- any patient not judged suitable for the study by the investigators
- women who are taking combination oral contraceptive

Study Enrollment

Patients meeting all of the inclusion and exclusion criteria will undergo standard treatment of their chronic subdural hematoma including operative treatment with the addition of preoperative and postoperative oral tranexamic acid treatment. Patients will receive a dose of 1300mg orally three to four hours prior to surgery. They will then take 1300mg orally three times daily for three days or until discharge, whichever occurs first. Tracking and follow-up will be explained to the patients and arranged by the study coordinator.

Tranexamic acid for cSDH – A Pilot Study on the Safety of Tranexamic Acid for the Chronic Subdural Hematoma Population

Study Interventions

All patients will undergo an intervention for the drainage of their subdural hematoma. The type of procedure i.e. burr-hole drainage or craniotomy excluding twist drill craniostomy will be at the discretion of the treating physician

All patients will be followed daily during their hospitalization

All patients will have follow-up CTs on postop days 1, 3, 7 and 30 +/- 7 days

All patients will have clinical follow-up on Day 30 +/- 7 days

All patients will be treated using standard ICU protocols

- neurologic status will be assessed at least every four hours for the first 48 hours
- care will be directed toward the goal of normotension and adequate oxygenation

All patients will have DVT prophylaxis with spontaneous compression devices. Pharmacologic prophylaxis will be at the discretion of the treating physician.

Experimental Interventions

Patients will receive tranexamic acid in the following dosing regimen:

1. 1300 mg times one immediately prior to surgery
2. 1300 mg orally three times daily for three days or until discharge- whichever comes first.

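### The only time-course test pools the preoperative scan with the postoperative ones, so after a large drop at surgery its P value cannot show whether the hematoma stays drained

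*Combined protocol and SAP*

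**What the plan says.** The Statistical Data Analysis section has one sentence that tests across time: "P values for difference among time point means (preoperative, postoperative days 3, 7 and 30) to be determined by ANOVA". It does not say which variable is analysed, whether the ANOVA is within patient, or which contrasts follow it. For summaries it says "Descriptive analyses of central tendency (mean) will be used for continuous variables", and it plans frequencies for ordinal and categorical variables. Other tests are named generically and tied to no endpoint.

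The End Points list includes "2* Postop hematoma expansion, functional outcome (mRS, NIHSS) discharge location, LOS, volume of hematoma at 30 days". Data Points includes "immediate postop hematoma width" and "width of hematoma on follow up imaging". The functional scales are recorded only twice ("NIH stroke scale Day 0 and 30, mRS day 0 and 30"), so they cannot fill the four time points, and width is the likeliest variable.

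Study Interventions states: "All patients will undergo an intervention for the drainage of their subdural hematoma". That section schedules CTs on postoperative Days 1, 3, 7 and 30. Clinical and Laboratory Evaluations lists Days 1, 14 and 30 after surgery. Day 1 is on both schedules but not in the ANOVA.

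**The concern.** The preoperative mean is one of the four being compared, and surgery is meant to move every later mean away from it. A significant overall result can come from drainage alone. The question that matters after surgery is whether the hematoma stays drained or re-accumulates, and that lies among the postoperative scans, which this test does not isolate.

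The expansion endpoint does not fill the gap as written. It has no cut-off and no reference scan, and the natural reference, Day 1, is outside the only time-course test.

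This matters because of the study's stated purpose: "This study intends to be a prerequisite to a large nationally funded randomized control trial". Planning that trial would call for the proportion of patients who expand, with its uncertainty, and the SD of change. An overall P value and a set of means supply neither.

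**Working it through.** **Inputs from the documents.** n=50 (Study Design); four time points and a 0.05 threshold (Statistical Data Analysis); 33% as the upper cited recurrence rate (Background). The plan gives no power or precision figure, so there is none to reproduce.

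**Assumptions.** SD 5 or 8 mm; drop at surgery 3, 5 or 10 mm; equal correlation of 0.3, 0.5 or 0.8 between scans; any regain appears at Day 30.

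**1. Algebra.** Let the means be (D, 0, 0, x), where D is the drop and x the mean regain at Day 30. The between-time sum of squares per patient is

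S = 0.75D² + 0.75x² − 0.5Dx.

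- Flat course (x = 0): S = 0.75D².
- 33% of patients regain the full drop (x = 0.33D): S = (0.75 + 0.082 − 0.165)D² = 0.667D², a fall of 11%.
- S is lowest at x = D/3, returns to the flat value at x = 2D/3 and exceeds it beyond that.

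The part of S due to preoperative versus the mean of the three postoperative times is 0.75(D − x/3)². At x = 0.33D this is 0.75 × 0.89² × D² = 0.594D², and 0.594/0.667 = 89% of the total.

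**2. Effect on the test.** For the within-patient F test, λ = nS/[SD²(1 − ρ)], with 3 and 147 degrees of freedom. At SD 8 mm, D = 5 mm and ρ = 0.5, the flat course gives λ = 50 × 0.75 × 25/(64 × 0.5) = 29.3. With 33% regaining, λ = 50 × 0.667 × 25/32 = 26.0. Both give power above 99%.

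Simulation (20,000 trials per setting, ρ = 0.5, each patient independently regaining the full drop or none of it) gives these chances of P<0.05, as ordinary / within-patient ANOVA:

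| SD, drop | Flat course | 33% regain the drop |
|---|---|---|
| 5 mm, 5 mm | 100% / 100% | 100% / 100% |
| 5 mm, 3 mm | 92% / 99.6% | 86% / 98.8% |
| 8 mm, 5 mm | 94% / 99.7% | 90% / 99.3% |
| 8 mm, 3 mm | 33% / 78% | 27% / 71% |

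Over all 18 settings, 33% regain lowers the rate by 0 to 7 points. At 80% regaining (SD 8 mm, drop 3 mm) the ordinary rate instead rises from about 33% to 39%, as the algebra predicts.

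**3. When drainage dominates.** With a linear rise of 0.2 to 0.5 SD from Day 3 to Day 30, the preoperative-versus-postoperative share of the between-time variation is 97% to 77% for a 1 SD drop and 99% to 95% for a 2 SD drop. For a 0.3 SD drop it is 60% to 1.5%. The statement that the P value mainly reflects surgery therefore needs a drop of about 1 SD or more.

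**4. What a Day 30 minus Day 1 change gives.** The 95% CI half-width is t(0.975, 49) × SD × √(2(1 − ρ)/50). At ρ = 0.5 with no regain, this is 2.01 × 5 × 0.141 = 1.4 mm, or 2.3 mm at SD 8 mm (0.9 to 2.7 mm over the range assumed). The paired t test is significant in 5% of trials when the course is flat. When 33% regain 5 mm it is significant in 54% (SD 5 mm) or 28% (SD 8 mm); when 10% do, in 10% or 7%.

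**5. What a count gives.** Exact 95% CIs: 17/50, 21.2% to 48.8%; 5/50, 3.3% to 21.8%; 0/50, 0% to 7.1%. The cut-off must be set in advance: at SD 5 mm and ρ = 0.5 the SD of change is 5 × √(2 × 0.5) = 5 mm, so about 16% of patients with no mean change would show growth of 5 mm or more.

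**6. Reoperation.** If 33% re-expand by 5 mm, all are reoperated and return to Day 1 width, and the others are unchanged, the Day 30 minus Day 1 mean is 0 mm. Using the last scan before reoperation, it is 0.33 × 5 = 1.65 mm.

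**The case against.** The best defence is that the plan never gives this ANOVA the job of detecting recurrence. The sentence names no endpoint, a test that includes the preoperative scan is a legitimate description of the course, and same-side reoperation is a separate endpoint. This stands. A reader might infer that the sponsor will offer the P value as evidence on recurrence or drug effect; nothing in the documents says so.

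A reader might also infer that expansion has no analysis at all. That goes too far: if expansion is scored yes/no, the planned frequencies would give a count. What is missing is the rule for scoring it and a confidence interval. Reported means would also show gross re-accumulation, though they could hide expansion in a minority.

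The plural in the ANOVA sentence could cover pairwise comparisons, including postoperative pairs. None is specified, and Day 1 would still be absent.

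Finally, it is tempting to say that re-expansion always makes significance less likely. Step 1 shows this fails once the mean regain passes two thirds of the drop.

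**Conclusion.** The point holds with a condition and a limited reach. If the drop at surgery is about 1 SD or more, the four-time P value mainly reflects drainage and cannot separate a hematoma that stays drained from one that re-accumulates: at SD 5 mm and a 5 mm drop the rate is 100% either way. Whether that condition is met cannot be shown from the documents, which give no SD, drop or correlation. At smaller drops the test is less dominated by surgery, but it still does not isolate postoperative change: at SD 8 mm and a 3 mm drop, re-expansion in a third of patients moves the rate by only 6 to 7 points.

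Independently of the drop, Day 1 is outside the test and expansion lacks a cut-off and reference scan. Only a secondary imaging endpoint is affected; the safety endpoint and return to the operating room are not. It should be fixed, but it does not threaten the study's main purpose.

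**What to change.** - Name the measure. Analyse postoperative scans only, within patient, with Day 1 as reference (for example a mixed model, or the paired Day 30 minus Day 1 change). Report the mean change with SD and 95% CI.
- Use the last scan before any reoperation, and state how later scans are handled.
- Prespecify the expansion cut-off from Day 1, set above ordinary scan-to-scan variation. Report the number and percentage of patients with an exact 95% CI, keeping return to the operating room as its own endpoint.
- Report the preoperative-to-postoperative change separately, as description. State that the four-time P value is not evidence about recurrence or, with one arm, about drug effect.
- Reconcile the two CT schedules (Days 3 and 7 in Study Interventions, Day 14 in Clinical and Laboratory Evaluations) so that the analysis days match the scans taken.

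The cost is SAP wording and a little more analysis. The Day 1 and Day 30 scans are on both schedules, and the methods are standard in R, which the plan already names. The downside is that the mean contrast has little power when few patients re-expand, so the estimates and intervals should be read rather than its P value.
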